4.4.2. Adverse Events

Adverse events will be analyzed in terms of treatment-emergent adverse events (TEAEs) which are defined as any AEs that begin or worsen on or after the start of study drug through 30 days after the last dose of study drug.

A treatment-related TEAE is defined as a TEAE that was considered by the Investigator to be at least possibly related to the study drugs.

If a subject experiences the same AE more than once with different toxicity grades, the event with the highest grade will be tabulated in the “by grade” tables. If a subject experiences multiple AEs under the same preferred term (SOC), the subject will be counted only once for that preferred term (SOC). In addition, AEs with a missing severity will be presented in the summary table as an intensity category of “Missing.”

An overall summary table presenting the number of subjects who experienced the following will be presented by treatment arm: any AE, any related AE, any severe AE, any serious AE, any serious related AE, any AE leading to discontinuation of study drug, and any AE leading to study discontinuation.

The incidence of TEAEs will be summarized by MedDRA SOC and preferred term. Tables summarizing the incidence of TEAEs will be generated for each of the following:

- All TEAEs
- TEAEs reported as treatment-related
- Severe or Grade 3/4 TEAEs

If no subjects experience any of the events in the overall summary table, the corresponding table by SOC and preferred term will not be produced.

No formal hypothesis-testing analysis of AE incidence rates will be performed.

All AEs occurring on-study will be listed in subject data listings.

By-subject listings also will be provided for the following: subject deaths, serious AEs, and AEs leading to withdrawal.

4.4.3. Laboratory Data

Clinical laboratory values will be expressed in the units reported by the central laboratory.

The actual value and change from baseline (Day 1) to Day 28 will be summarized for each clinical chemistry parameter. In the event of repeat values, the last non-missing value per visit will be used.

All laboratory data will be provided in data listings. Values outside of the lab parameter’s normal range will be flagged as high, low, or abnormal based on the range of the test.

4.4.4. Vital Signs and Physical Examination

Vital sign measurements will be presented for each subject in a data listing. Systolic blood pressure, diastolic blood pressure, heart rate, and weight will be summarized as actual value and change from baseline by visit. If the safety population is identical to the ITT population, summaries of blood pressure will not be included in these tables because this will be produced for the primary endpoint as described under the efficacy analysis.

All physical examination findings will be presented in a data listing.

4.4.5. **Electrocardiogram**

Electrocardiogram results will be summarized descriptively, including the number and percentage of subjects with normal, abnormal, and clinically significant abnormal results at baseline and at Day 28.

Electrocardiogram data for each subject will be provided in a data listing.

4.4.6. **Concomitant Medications**

Concomitant medications will be coded using the WHO Drug Dictionary. Results will be tabulated by anatomic therapeutic class (ATC) and preferred term.

Concomitant medications will be tabulated by treatment group, where any medications that did not end prior to first dose will be included. If an end date is missing or the medication is ongoing, the medication will be included.

The use of concomitant medications will be included in a by-subject data listing.

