## **12.4 12-lead Electrocardiograms**

Standard safety 12-lead ECGs will be performed at Screening and Week 4.

Standard 12-lead ECGs will be performed according to the site SOPs. ECGs should be performed after the subject has been resting supine for  $\geq$  5 minutes. The ECG will include all 12 standard leads and a Lead II rhythm strip on the bottom of the tracing. The ECG will be recorded at a paper speed of 25 mm/sec. The following ECG parameters will be collected: PR interval, QRS interval, QT interval, and QTc interval (QTcB; Bazett's correction). All ECGs must be evaluated by a qualified physician for the presence of abnormalities.

If clinically significant abnormalities are found, the study subject will NOT be allowed into the study.

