DATE: HH:MM/DDMMYYYY

PROGRAMMING NOTE: Continue for all chemistry parameters.

Repeat for:

Table 14.3.5.2 Summary of Values and Change from Baseline for Vital Parameters (Safety Population)

Table 14.3.5.3

Electrocardiogram - Shift in Interpretation from Baseline to Day 28 (Safety Population)

Treatment	Interpretation	Baseline n	Day 28 Visit					Total n (%)
			Normal n (%)	Abnormal, NCS n (%)	Abnormal, CS n (%)	Missing n (%)		
B244	Normal	xx	xx (xx.x)	xx (xx.x)	xx (xx.x)	xx (xx.x)	xx (xx.x)	xx (xx.x)
	Abnormal, NCS	xx	xx (xx.x)	xx (xx.x)	xx (xx.x)	xx (xx.x)	xx (xx.x)	xx (xx.x)
	Abnormal, CS	xx	xx (xx.x)	xx (xx.x)	xx (xx.x)	xx (xx.x)	xx (xx.x)	xx (xx.x)
	Missing	xx	xx (xx.x)	xx (xx.x)	xx (xx.x)	xx (xx.x)	xx (xx.x)	xx (xx.x)
	Total	xx	xx (xx.x)	xx (xx.x)	xx (xx.x)	xx (xx.x)	xx (xx.x)	xx (xx.x)
Placebo	<as above>							

Source: [Listing 16.2.9.2](#)

PROGRAM NAME: XXXXXXXXXXXXXXXXXXXXXXXXXXXXXXXXX

DATE: HH:MM/DDMMYYYY

[figure not shown]

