Listing 16.2.8.2.2 Chemistry - Part 2

AOBiome LLC
Protocol AVB244-003

Confidential

Page 1 of x

Listing 16.2.8.3

Urine Pregnancy Test

Treatment:

Strata:

Subject Number	Visit	Date Performed	Rel Day	Pregnancy Test Done?	Reason Not Done	Test Result
					Not Childbearing	Positive
					Potential Female	Negative
					Other	

Rel Day = Relative to first dose of study medication, Day 1.

PROGRAM NAME: XXXXXXXXXXXXXXXXXXXXXXXXXXXXXXXXXXXXXXX

DATE: HH:MM/DDMMYYYY

PROGRAMMING NOTE: Report for females only.

AOBiome LLC
Protocol AVB244-003

Confidential

Page 1 of x

Listing 16.2.9.1

Vital Signs

Treatment:
Strata:

Subject Number	Visit	Date/ Time of Collection	Rel Day	Diastolic Blood Pressure (mmHg)	Heart Rate (BPM)	Weight (kg)
----------------	-------	--------------------------------	---------	---------------------------------	------------------	-------------

Rel Day = Relative to first dose of study medication, Day 1.

PROGRAM NAME: XXXXXXXXXXXXXXXXXXXXXXXXXXXXXXXXX

DATE: HH:MM/DDMMYYYY

AOBiome LLC
Protocol AVB244-003

Confidential

Page 1 of x

Listing 16.2.9.2

12-Lead Electrocardiogram

Treatment:

Strata:

Subject Number	Date Performed	Rel Day	Resting Supine for >5 Minutes?	PR Interval (msec)	QRS Interval (msec)	QT Interval (msec)	RR Interval (msec)	QTc Interval (QTcB; Bazett's correction) (sec)	Assessment
									Normal
									Abnormal, NCS
									Abnormal, CS

CS = Clinically Significant, NCS = Abnormal, Not Clinically Significant.

PROGRAM NAME: XXXXXXXXXXXXXXXXXXXXXXXXXXXXXXXXX

DATE: HH:MM/DDMMYYYY

AOBiome LLC
Protocol AVB244-003

Confidential

Page 1 of x

Listing 16.2.9.3

Soap and Shampoo

Treatment:

Strata:

Subject Number	Visit	Date of Follow-up	Rel Day	Consis- tently [1] Using Provided	Other Soap and Shampoo?	If No, Soap Shampoo? Reason	Used	Fre- quency Since Last Visit	Sponsor- Provided Soap/ Shampoo Since Moving Forward? Visit	Plan to Use Refrain- ing from Moving Use?	If No, Days per Week of Moving Use?	Compliant With IP Return Remaining Soap/ Shampoo?	Number of Missed Since Last Visit?	
				Yes				<5			1-2			
				No				Times			Days			
								5-10			2-4			
								Times			Days			
								>10			4+			
								Times			Days			

[1] Consistently meaning they have not used any other soap or shampoo more than once or twice since the last visit.

PROGRAM NAME: XXX

DATE: HH:MM/DDMMYYYY

AOBiome LLC
Protocol AVB244-003

Confidential

Page 1 of x

Listing 16.2.9.4

Concomitant Medications

Treatment:
Strata:

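### ECG intervals are collected at Screening and Week 4, but no planned table gives their values or change by arm, so a small or moderate mean shift could go unnoticed in the tables

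*SAP*

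**What the plan says.** Protocol 12.4 sets the timing: "Standard safety 12-lead ECGs will be performed at Screening and Week 4". It then lists the measurements: "The following ECG parameters will be collected: PR interval, QRS interval, QT interval, and QTc interval", the last with Bazett's correction. On reading the traces it says: "All ECGs must be evaluated by a qualified physician for the presence of abnormalities". It gives no numeric limit for calling an interval abnormal.

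SAP 4.4.5 plans a descriptive summary, "including the number and percentage of subjects with normal, abnormal, and clinically significant abnormal results at baseline and at Day 28", and a by-subject listing. The output list and shells in SAP 7.1 contain one ECG table and one ECG listing:

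- Table 14.3.5.3 cross-tabulates the baseline and Day 28 interpretation (normal; abnormal, not clinically significant; abnormal, clinically significant; missing). It has one block for B244 and one for placebo.
- Listing 16.2.9.2 prints PR, QRS, QT, RR and QTcB for each subject, with the date, relative day and assessment.

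**The concern.** Safety and tolerability is a primary objective, and the ECG intervals are continuous measurements taken before and at the end of treatment. Yet the only planned between-arm view of them is through a judgement on the whole trace. If an interval moves in most subjects but stays inside normal limits, the interpretation need not change, and the shift table can look the same in both arms.

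The intervals are in the listing, but a listing of about 116 subjects gives no mean, no change and no difference between arms. At stake is the weight of the ECG statement in the study report. A conclusion of no ECG effect would rest on a display that is not built to show a modest average change. Because the B244 subjects are pooled, a pattern by spray count would not be visible in that table either.

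**Working it through.** **Step 1. What each safety measure gets in the SAP.**

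| Measure | Value and change by arm? | 4 and 8 sprays shown separately? | Where |
|---|---|---|---|
| Chemistry | Yes | Yes | SAP 4.4.3, Table 14.3.5.1 |
| Heart rate, weight | Yes | Yes | SAP 4.4.4, Table 14.3.5.2 (repeats the 14.3.5.1 layout) |
| Adverse events | Counts, not continuous | Yes | Tables 14.3.1.1 and 14.3.1.2 |
| ECG interpretation | Shift table | No, B244 pooled | Table 14.3.5.3 |
| ECG intervals | No | No | Listing 16.2.9.2 only |

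SAP 3.2 also has a general rule that continuous variables get n, mean, median, SD, minimum and maximum. No ECG shell applies it. So the gap lies in the output list and shells; the wording of SAP 4.4.5 would allow more than they deliver.

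**Step 2. The sample size used for illustration.** The documents contain no ECG figure to reproduce. The 52 per arm comes from SAP 3.1 and the two-sided 0.05 from SAP 3.2. As a check on the method, SAP 3.1 states 80% power for 5.8 mmHg with SD 10.5. The standardised effect is 5.8/10.5 = 0.552. The standard error in SD units is sqrt(2/52) = 0.1961, so the noncentrality is 0.552/0.1961 = 2.82 and the t-test power is 79.7%. With SD 9 it is 0.644/0.1961 = 3.29, giving 90.2%. Both match the SAP.

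**Step 3. Means against counts past a cut.** Everything about the ECG here is an assumption: the shift d in SD units, and the share p0 of placebo subjects beyond a cut. The interpretation is simplified to a single cut on one interval.

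- Means: two-sample t-test with noncentrality d/0.1961.
- Counts: the rate on B244 is p1 = P(Z > z(1-p0) - d). For d = 0.5 this gives 5% v 12.6%, 10% v 21.7% and 20% v 36.6%. Power is by exact binomial enumeration of the pooled two-proportion z-test at 1.96.

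| Shift d (SD) | Means | Cut at 5% | Cut at 10% | Cut at 20% |
|---|---|---|---|---|
| 0.4 | 52.4% | 17.7% | 24.6% | 32.8% |
| 0.5 | 71.4% | 27.1% | 37.1% | 47.9% |
| 0.6 | 85.8% | 39.0% | 51.8% | 63.5% |
| 1.0 | 99.9% | 87.6% | 95.0% | 97.8% |

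With Fisher's exact test the 0.5 SD row for the cuts falls to 15%, 28% and 38%. The gap is wide for modest shifts and nearly closes at 1.0 SD.

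**Step 4. The same in milliseconds, again on assumed inputs.** Take an SD of QTc change of 15 to 25 ms for the means, and for the counts a between-subject SD of 15 to 25 ms with 2% to 10% abnormal on placebo (Fisher's test).

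| True shift | Means | Counts |
|---|---|---|
| 5 ms | 17-39% | 0.2-11% |
| 10 ms | 52-92% | 2-53% |
| 20 ms | 98-100% | 24-99.7% |
| 30 ms | about 100% | 79-100% |

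The 95% CI half-width for the arm difference would be 1.983 x 0.1961 x SD = 0.389 SD, that is 5.8 to 9.7 ms. So a mean-change table has limited sensitivity of its own at 5 ms. What it adds is an estimate with its uncertainty.

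**The case against.** The case against making much of this is substantial, and most of it stands.

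- **No ECG test is planned.** SAP 3.2 confines formal testing to the primary and secondary efficacy endpoints, and SAP 4.4.5 is descriptive. The power figures therefore compare two tests the plan does not contain. They stand only as a comparison of how much information each display carries.
- **The model is not the planned table.** Table 14.3.5.3 pairs baseline with Day 28 over several categories, and a physician's reading covers findings that intervals do not measure. A one-time cut on one interval is a simplification.
- **Nothing promised is missing.** The declared safety endpoint is adverse events. Protocol 15.3 and SAP 3.2 name laboratory values and vital signs, not ECGs, for value-and-change summaries.
- **Other outputs help.** Every interval is listed by subject, and heart rate is summarised. A new abnormal sign can be an adverse event under Protocol 16.1, and adverse events are tabulated by spray count.

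A reader might infer that a drug-related interval shift would very likely be missed. The documents do not support that. They give no shift size, SD, abnormal rate or numeric reading rule, and in the illustration large shifts usually show. A reader might also think that barring clinically significant ECG abnormalities at entry (Protocol 12.4) makes the table blinder. It does not follow: a new clinically significant reading at Day 28 would stand out more against such a baseline. Nor does SAP 4.4.5 limit the summary to categories; its wording is open, and it is the shells that stop there.

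What survives is narrow. Continuous ECG data are collected and never summarised by arm, unlike the other continuous safety measures in Step 1, and the SAP gives no reason.

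**Conclusion.** The point holds as a gap in safety reporting. The planned tables show ECGs by arm only through overall interpretation, with B244 pooled, so a small or moderate mean change in an interval, within normal limits, could pass unseen in the tables. Large changes would probably still appear.

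Its size cannot be fixed from the documents. On the assumptions above, at 0.5 SD the counts have 23 to 44 percentage points less power than the means (71.4 - 47.9 = 23.5; 71.4 - 27.1 = 44.3). At 1.0 SD the difference is about 2 to 12 points (99.9 - 97.8 = 2.1; 99.9 - 87.6 = 12.3). These numbers rest on assumed shifts, rates and SDs and on treating the interpretation as one cut.

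The conclusion itself rests only on the output list and shells. It does not touch the efficacy analysis, and it is no departure from the protocol. It is worth acting on because safety is a primary objective and the improvement is cheap.

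**What to change.** In SAP 4.4.5 and the table list, add one descriptive ECG interval table in the Table 14.3.5.1 layout:

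- Parameters: PR, QRS, QT, QTcB and RR. The first four are in Protocol 12.4; RR is in Listing 16.2.9.2.
- Content: value at Screening and at Day 28, and the change. Label the baseline as Screening, since that is the only scheduled ECG before dosing.
- Columns: 4 sprays, 8 sprays, All B244 and Placebo.
- For each interval, the B244-minus-placebo difference in mean change with a 95% CI, labelled as an unadjusted, descriptive safety estimate. Adjustment for the baseline interval is optional.

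Keep Table 14.3.5.3. Splitting its B244 rows by spray count is optional, since the pooled comparison is the one the trial is sized for.

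The cost is one more table and a sentence in SAP 4.4.5, from data and a shell that already exist, with no new procedure or patient. The downside is five more parameters with CIs not adjusted for multiplicity, where an isolated interval excluding zero could be over-read; the label should say so. The difference with a CI also goes a step beyond what the SAP gives for chemistry and vital signs. If the sponsor wants strict uniformity, value and change by arm alone would close most of the gap.

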5. CHANGES TO PLANNED ANALYSES

The following changes between the study protocol are described below.

Editorial edits have been made in [Section 1.1.1](#) (Introduction), [Section 1.2.1](#) (Synopsis of Study Design), [Section 1.2.2](#) (Randomization Methodology), and [Section 1.2.5](#) (Efficacy Parameters) to clarify the information from the study protocol.

The schedule of events was changed according to an administrative letter from AOBiome dated 08 February 2017. Subjects were instructed to continue use of IP through end of the ABPM monitoring period (Day 29 [Visit 4B] and to weigh the IP after this visit. Subjects who had already completed the Day 29 visit prior to the notification should have used the IP through Day 28 and weighed the product on this visit.

The SD in the sample size was changed from 11 to 10.5 in order to estimate power correctly.

7.1.1. Statistical Table Shells

The following tables will be produced.

STATISTICAL TABLES

Table 14.1.1

Subject Enrollment and Disposition (All Enrolled Subjects)

Disposition	Statistic	B244		Placebo		Overall (N=xx)
		4 Sprays (N=xx)	8 Sprays (N=xx)	4 Sprays (N=xx)	8 Sprays (N=xx)	
Total Number of Subjects						
Screened	n (%)	xx (xx.x)	xx (xx.x)	xx (xx.x)	xx (xx.x)	xx (xx.x)
Screen Failures [1]	n (%)	xx (xx.x)	xx (xx.x)	xx (xx.x)	xx (xx.x)	xx (xx.x)
Enrolled [1]	n (%)	xx (xx.x)	xx (xx.x)	xx (xx.x)	xx (xx.x)	xx (xx.x)
Randomized [1]	n (%)	xx (xx.x)	xx (xx.x)	xx (xx.x)	xx (xx.x)	xx (xx.x)
Treated [2]	n (%)	xx (xx.x)	xx (xx.x)	xx (xx.x)	xx (xx.x)	xx (xx.x)
Completed the Study [3]	n (%)	xx (xx.x)	xx (xx.x)	xx (xx.x)	xx (xx.x)	xx (xx.x)
Discontinued	n (%)	xx (xx.x)	xx (xx.x)	xx (xx.x)	xx (xx.x)	xx (xx.x)
Study Population [4]						
Safety	n (%)	xx (xx.x)	xx (xx.x)	xx (xx.x)	xx (xx.x)	xx (xx.x)
Intent-to-Treat (ITT)	n (%)	xx (xx.x)	xx (xx.x)	xx (xx.x)	xx (xx.x)	xx (xx.x)
Per Protocol (PP)	n (%)	xx (xx.x)	xx (xx.x)	xx (xx.x)	xx (xx.x)	xx (xx.x)
Ambulatory Blood Pressure	n (%)	xx (xx.x)	xx (xx.x)	xx (xx.x)	xx (xx.x)	xx (xx.x)
Strata						
Pre-Hypertension	n (%)	xx (xx.x)	xx (xx.x)	xx (xx.x)	xx (xx.x)	xx (xx.x)
Stage 1 Hypertension	n (%)	xx (xx.x)	xx (xx.x)	xx (xx.x)	xx (xx.x)	xx (xx.x)
Reason for Early Study Discontinuation						
Death	n (%)	xx (xx.x)	xx (xx.x)	xx (xx.x)	xx (xx.x)	xx (xx.x)
Lost to follow-up	n (%)	xx (xx.x)	xx (xx.x)	xx (xx.x)	xx (xx.x)	xx (xx.x)
Withdrawal of consent by subject	n (%)	xx (xx.x)	xx (xx.x)	xx (xx.x)	xx (xx.x)	xx (xx.x)
Investigator's decision	n (%)	xx (xx.x)	xx (xx.x)	xx (xx.x)	xx (xx.x)	xx (xx.x)
Screen Failure	n (%)	xx (xx.x)	xx (xx.x)	xx (xx.x)	xx (xx.x)	xx (xx.x)
Other	n (%)	xx (xx.x)	xx (xx.x)	xx (xx.x)	xx (xx.x)	xx (xx.x)

[1] Percentage based on the number screened.

[2] Percentage based on the number enrolled.

[3] Percentage and all subsequent percentages based on the number dosed.

[4] Safety Population: All subjects who received at least 1 dose of study medication, analyzed according to drug received.

Intent-to-Treat (ITT) Population: all randomized subjects, analyzed according to treatment assigned.

Per Protocol (PP) Population: Subjects who were administered at least 50% of , have baseline and at least 1 post-baseline in-clinic systolic or diastolic blood pressure measurement, and did not have any major protocol violations which could potentially compromise interpretation of results.

Ambulatory Blood Pressure Monitoring Population (ABPM): Subjects in the Safety population who had valid baseline and Day 28 ABPM measurements. Subjects who repeated the ABPM are included in the population if the repeated assessment met the Monitor's criteria for "passing."

Source: [Listing 16.2.1](#)

Table 14.1.2.1A

Demographics and Baseline Characteristics (ITT Population)

Parameter	Statistic	B244		Placebo		Overall (N=xx)
		4 Sprays (N=xx)	8 Sprays (N=xx)	4 Sprays (N=xx)	8 Sprays (N=xx)	
Age (years)	n	xx	xx	xx	xx	xx
	Mean (SD)	xx.x (xx.xx)	xx.x (xx.xx)	xx.x (xx.xx)	xx.x (xx.xx)	xx.x (xx.xx)
	Median	xx.x	xx.x	xx.x	xx.x	xx.x
	Min, Max	xx, xx	xx, xx	xx, xx	xx, xx	xx, xx
	P-value [1]					0.xxxxx
Age Category (years)	n (%)	xx (xx.x)	xx (xx.x)	xx (xx.x)	xx (xx.x)	xx (xx.x)
<60	n (%)	xx (xx.x)	xx (xx.x)	xx (xx.x)	xx (xx.x)	xx (xx.x)
>=60						0.xxxxx
	P-value [2]					
Sex	n (%)	xx (xx.x)	xx (xx.x)	xx (xx.x)	xx (xx.x)	xx (xx.x)
Female	n (%)	xx (xx.x)	xx (xx.x)	xx (xx.x)	xx (xx.x)	xx (xx.x)
Male	n (%)	xx (xx.x)	xx (xx.x)	xx (xx.x)	xx (xx.x)	xx (xx.x)
	P-value [2]					0.xxxxx
Race						
American Indian or Alaska Native	n (%)	xx (xx.x)	xx (xx.x)	xx (xx.x)	xx (xx.x)	xx (xx.x)
Asian	n (%)	xx (xx.x)	xx (xx.x)	xx (xx.x)	xx (xx.x)	xx (xx.x)
Black or African	n (%)	xx (xx.x)	xx (xx.x)	xx (xx.x)	xx (xx.x)	xx (xx.x)
American	n (%)	xx (xx.x)	xx (xx.x)	xx (xx.x)	xx (xx.x)	xx (xx.x)
Native Hawaiian or Other Pacific Islander	n (%)	xx (xx.x)	xx (xx.x)	xx (xx.x)	xx (xx.x)	xx (xx.x)
White	n (%)	xx (xx.x)	xx (xx.x)	xx (xx.x)	xx (xx.x)	xx (xx.x)
Other	n (%)	xx (xx.x)	xx (xx.x)	xx (xx.x)	xx (xx.x)	xx (xx.x)
Ethnicity						
Hispanic/Latino	n (%)	xx (xx.x)	xx (xx.x)	xx (xx.x)	xx (xx.x)	xx (xx.x)
Not Hispanic/Latino	n (%)	xx (xx.x)	xx (xx.x)	xx (xx.x)	xx (xx.x)	xx (xx.x)
Unknown	n (%)	xx (xx.x)	xx (xx.x)	xx (xx.x)	xx (xx.x)	xx (xx.x)

[1] P-value is from ANCOVA model.

[2] P-value is from Cochran-Mantel-Haenszel test.

Source: [Listing 16.2.4.1](#)

PROGRAM NAME: XXX

DATE: HH:MM/DDMMYYYY

Table 14.1.2.1A

Demographics and Baseline Characteristics (ITT Population)

Parameter	Statistic	B244		Placebo		Overall (N=xx)
		4 Sprays (N=xx)	8 Sprays (N=xx)	4 Sprays (N=xx)	8 Sprays (N=xx)	
Weight (kg)	n	xx	xx	xx	xx	xx
	Mean (SD)	xx.x (xx.xx)	xx.x (xx.xx)	xx.x (xx.xx)	xx.x (xx.xx)	xx.x (xx.xx)
	Median	xx.x	xx.x	xx.x	xx.x	xx.x
	Min, Max	xx, xx	xx, xx	xx, xx	xx, xx	xx, xx
BMI (kg/m ²)	n	xx	xx	xx	xx	xx
	Mean (SD)	xx.x (xx.xx)	xx.x (xx.xx)	xx.x (xx.xx)	xx.x (xx.xx)	xx.x (xx.xx)
	Median	xx.x	xx.x	xx.x	xx.x	xx.x
	Min, Max	xx, xx	xx, xx	xx, xx	xx, xx	xx, xx
	p-value [1]					0.xxxx
BMI Category (kg/m ²)						
<30	n (%)	xx (xx.x)	xx (xx.x)	xx (xx.x)	xx (xx.x)	xx (xx.x)
≥30	n (%)	xx (xx.x)	xx (xx.x)	xx (xx.x)	xx (xx.x)	xx (xx.x)
Smoking History						
Never	n (%)	xx (xx.x)	xx (xx.x)	xx (xx.x)	xx (xx.x)	xx (xx.x)
Former	n (%)	xx (xx.x)	xx (xx.x)	xx (xx.x)	xx (xx.x)	xx (xx.x)
Current	n (%)	xx (xx.x)	xx (xx.x)	xx (xx.x)	xx (xx.x)	xx (xx.x)

[1] P-value is from ANCOVA model.

[2] P-value is from Cochran-Mantel-Haenszel test.

Source: [Listing 16.2.4.1](#), [Listing 16.2.4.2](#)

PROGRAM NAME: XXXXXXXXXXXXXXXXXXXXXXXXXXXXXXXXX

DATE: HH:MM/DDMMYYYY

Repeat for:

Table 14.1.2.1B Demographics and Baseline Characteristics (PP Population)

Table 14.1.3.1A

Concomitant Medication by Anatomic Therapeutic Class and Preferred Term (ITT Population)

Parameter	Statistic	B244		Placebo		Overall (N=xx)
		4 Sprays (N=xx)	8 Sprays (N=xx)	4 Sprays (N=xx)	8 Sprays (N=xx)	
ATC 1						
PT 1	n (%)	xx (xx.x)	xx (xx.x)	xx (xx.x)	xx (xx.x)	xx (xx.x)
PT 2	n (%)	xx (xx.x)	xx (xx.x)	xx (xx.x)	xx (xx.x)	xx (xx.x)
Etc.						
ATC 2						
PT 1	n (%)	xx (xx.x)	xx (xx.x)	xx (xx.x)	xx (xx.x)	xx (xx.x)
PT 2	n (%)	xx (xx.x)	xx (xx.x)	xx (xx.x)	xx (xx.x)	xx (xx.x)
Etc.						
Etc.						

Note: Concomitant medications are any medications that did not end prior to first dose. If an end date is missing or the medication is ongoing, the medication is included.

Note: Concomitant medications anatomic therapeutic class (ATC) and preferred term (PT) are coded using the WHO Drug Dictionary version March 2016.

Source: [Listing 16.2.9.4](#)

PROGRAM NAME: XXXXXXXXXXXXXXXXXXXXXXXXXXXXXXXXXXXXXXX

DATE: HH:MM/DDMMYYYY

Repeat for:

Table 14.1.3.1B Concomitant Medication by Anatomic Therapeutic Class and Preferred Term (PP Population)

Table 14.1.4.1A

Summary of Drug Exposure (ITT Population)

Parameter	Statistic	B244		Placebo		Overall (N=xx)
		4 Sprays (N=xx)	8 Sprays (N=xx)	4 Sprays (N=xx)	8 Sprays (N=xx)	
Cumulative Study Drug Exposure (g) [1]	n	xx	xx	xx	xx	xx
	Mean (SD)	xx.x (xx.xx)	xx.x (xx.xx)	xx.x (xx.xx)	xx.x (xx.xx)	xx.x (xx.xx)
	Median	xx.x	xx.x	xx.x	xx.x	xx.x
	Min, Max	xx, xx	xx, xx	xx, xx	xx, xx	xx, xx
Amount of Product Used per Day (g) [2]	n	xx	xx	xx	xx	xx
	Mean (SD)	xx.x (xx.xx)	xx.x (xx.xx)	xx.x (xx.xx)	xx.x (xx.xx)	xx.x (xx.xx)
	Median	xx.x	xx.x	xx.x	xx.x	xx.x
	Min, Max	xx, xx	xx, xx	xx, xx	xx, xx	xx, xx
Days of Study Drug Administration	n	xx	xx	xx	xx	xx
	Mean (SD)	xx.x (xx.xx)	xx.x (xx.xx)	xx.x (xx.xx)	xx.x (xx.xx)	xx.x (xx.xx)
	Median	xx.x	xx.x	xx.x	xx.x	xx.x
	Min, Max	xx, xx	xx, xx	xx, xx	xx, xx	xx, xx
Percent Compliance [3]	n	xx	xx	xx	xx	xx
	Mean (SD)	xx.x (xx.xx)	xx.x (xx.xx)	xx.x (xx.xx)	xx.x (xx.xx)	xx.x (xx.xx)
	Median	xx.x	xx.x	xx.x	xx.x	xx.x
	Min, Max	xx, xx	xx, xx	xx, xx	xx, xx	xx, xx

[1] Cumulative study drug exposure = weight of the 3 drug bottles at last visit - weight of the 4 drug bottles at first dispense.

[2] Amount of product used per day = change / number of days the subject was on treatment.

[3] Percent compliance = (Net weight of study drug) / (Expected net weight for 28 days of use) × 100.

Source: [Listing 16.2.5.1](#), [Listing 16.2.5.2](#)

PROGRAM NAME: XXXXXXXXXXXXXXXXXXXXXXXXXXXXXXXXXXXXXXX

DATE: HH:MM/DDMMYYYY

Repeat for:

Table 14.1.4.1B Summary of Drug Exposure (PP Population)

Table 14.2.1A

Summary of Values and Change from Baseline for Systolic and Diastolic Blood Pressure - Mixed Model Analysis (ITT Population)

Parameter: Systolic Blood Pressure

Visit	Actual/ Change	Statistic	B244			
			4 Sprays (N=xx)	8 Sprays (N=xx)	All B244 (N=xx)	Placebo (N=xx)
Baseline	Actual	n	xx	xx	xx	xx
		Mean (SD)	xx.x (xx.xx)	xx.x (xx.xx)	xx.x (xx.xx)	xx.x (xx.xx)
		Median	xx.x	xx.x	xx.x	xx.x
		Min, Max	xx, xx	xx, xx	xx, xx	xx, xx
Day 7	Actual	n	xx	xx	xx	xx
		Mean (SD)	xx.x (xx.xx)	xx.x (xx.xx)	xx.x (xx.xx)	xx.x (xx.xx)
		Median	xx.x	xx.x	xx.x	xx.x
		Min, Max	xx, xx	xx, xx	xx, xx	xx, xx
	Change	n	xx	xx	xx	xx
		Mean (SD)	xx.x (xx.xx)	xx.x (xx.xx)	xx.x (xx.xx)	xx.x (xx.xx)
		Median	xx.x	xx.x	xx.x	xx.x
		Min, Max	xx, xx	xx, xx	xx, xx	xx, xx
		LS MEAN (SEM)	xx.x (xx.xx)	xx.x (xx.xx)	xx.x (xx.xx)	xx.x (xx.xx)
		95% CI	xx, xx	xx, xx	xx, xx	xx, xx
		LS MEAN Difference B244 - Placebo (SEM)	xx.x (xx.xx)	xx.x (xx.xx)	xx.x (xx.xx)	xx.x (xx.xx)
		95% CI	xx, xx	xx, xx	xx, xx	xx, xx
		P-value [1] (vs Placebo)	0.xx	0.xx	0.xx	0.xx
		P-value [1] (vs 8 Sprays)	0.xx			
Day 14		<as above in Day 7>				
Day 21		<as above>				
Day 28		<as above>				
Day 42		<repeat Actual and Change parameters only>				

Note: Day 42 is not included in model. In the mixed-effect model repeated measures (MMRM) model, the outcome variable is change from baseline in NIS-W. The model includes baseline blood pressure as covariate and fixed effect terms including treatment group, visit, treatment-by-visit interaction and hypertension status.

[1] P-value is derived from the contrast testing at each visit using the MMRM model.

Source: [Listing 16.2.6.1](#)

PROGRAM NAME: XXXXXXXXXXXXXXXXXXXXXXXXXXXXXXXXXXXXXXX

DATE: HH:MM/DDMMYYYY

PROGRAMMING NOTE: Continue for Diastolic Blood Pressure Mixed Model Analysis.

Repeat Table 14.2.1A for:

Table 14.2.1B Summary of Values and Change from Baseline for Systolic and Diastolic Blood Pressure - Mixed Model Analysis (PP Population)

Table 14.2.1C Summary of Values and Change from Baseline for Systolic and Diastolic Blood Pressure by Race - Mixed Model Analysis (ITT Population)

Table 14.2.1D Summary of Values and Change from Baseline for Systolic and Diastolic Blood Pressure by Hypertension Stage - Mixed Model Analysis (ITT Population)

Table 14.2.1E Summary of Values and Change from Baseline for Systolic and Diastolic Blood Pressure by Gender - Mixed Model Analysis (ITT Population)

Table 14.2.1F Summary of Values and Change from Baseline for Systolic and Diastolic Blood Pressure by Age Group - Mixed Model Analysis (ITT Population)

PROGRAMMING NOTE: Replace Visit with each subgroup as applicable per table title. P-values and LSMEANS are not required for any subgroups except hypertension stage.

Table 14.2.2A

Change from Baseline at Day 28 ANCOVA Model for Systolic and Diastolic Blood Pressure (ITT Population)

Parameter: Systolic Blood Pressure

		B244			
Visit	Statistic	4 Sprays (N=xx)	8 Sprays (N=xx)	All B244 (N=xx)	Placebo (N=xx)
Day 28	LS Mean (SE)	xx.x (xx.xx)	xx.x (xx.xx)	xx.x (xx.xx)	xx.x (xx.xx)
	95% CI	xx.x	xx.x	xx.x	xx.x
	LS Mean Difference (SE) (Placebo-Active)	xx.x (xx.xx)	xx.x (xx.xx)	xx.x (xx.xx)	
	95% CI for Mean Difference	Xx, xx	Xx, xx	Xx, xx	
	P-value (vs Placebo)	0.xxxxx	0.xxxxx	0.xxxxx	
	P-value (vs 8 Spray)	0.xxxxx			

LS: Least-squares. SE = Standard Error. CI = Confidence Interval.

Model: The ANCOVA model includes the change from baseline as the dependent variable, treatment and strata as factors and baseline value as a covariate.

Source: [Listing 16.2.6.1](#)

PROGRAM NAME: XXX

DATE: HH:MM/DDMMYYYY

PROGRAMMING NOTE: Continue for Diastolic Blood Pressure.

Repeat for:

Table 14.2.2B Change from Baseline at Day 28 ANCOVA Model for Systolic and Diastolic Blood Pressure (PP Population)

Table 14.2.2C Change from Baseline at Day 28 ANCOVA Model for Systolic and Diastolic Blood Pressure by Hypertension Stage (ITT Population)

Table 14.2.3A

Summary of Values and Change from Baseline for Ambulatory Blood Pressure (ABP Population)

Parameter: Systolic Blood Pressure

Parameter	Visit	Actual/Change	Statistic	4 Sprays (N=xx)	8 Sprays (N=xx)	Placebo (N=xx)
Daytime	Baseline	Actual	n	xx	xx	xx
			Mean (SD)	xx.x (xx.xx)	xx.x (xx.xx)	xx.x (xx.xx)
			Median	xx.x	xx.x	xx.x
			Min, Max	xx, xx	xx, xx	xx, xx
Daytime	Day 28	Actual	n	xx	xx	xx
			Mean (SD)	xx.x (xx.xx)	xx.x (xx.xx)	xx.x (xx.xx)
			Median	xx.x	xx.x	xx.x
			Min, Max	xx, xx	xx, xx	xx, xx
Daytime	Day 28	Change	n	xx	xx	xx
			Mean (SD)	xx.x (xx.xx)	xx.x (xx.xx)	xx.x (xx.xx)
			Median	xx.x	xx.x	xx.x
			Min, Max	xx, xx	xx, xx	xx, xx
Nighttime			n	xx	xx	xx
			Mean (SD)	xx.x (xx.xx)	xx.x (xx.xx)	xx.x (xx.xx)
			Median	xx.x	xx.x	xx.x
			Min, Max	xx, xx	xx, xx	xx, xx
24-hour			n	xx	xx	xx
			Mean (SD)	xx.x (xx.xx)	xx.x (xx.xx)	xx.x (xx.xx)
			Median	xx.x	xx.x	xx.x
			Min, Max	xx, xx	xx, xx	xx, xx

Source: [Listing 16.2.6.1](#)

PROGRAM NAME: XXX

DATE: HH:MM/DDMMYYYY

PROGRAMMING NOTE: Continue for Diastolic Blood Pressure and Mean Arterial Pressure. If the subject has results for more than 24 hours in a visit, only the first time point per hour will be included in the analysis. Repeat Daytime layout for Nighttime and 24-hour analysis.

Repeat for:

- Table 14.2.3B Summary of Values and Change from Baseline for Ambulatory Blood Pressure by Race (ABP Population)
- Table 14.2.3C Summary of Values and Change from Baseline for Ambulatory Blood Pressure by Hypertension Stage (ABP Population)
- Table 14.2.3D Summary of Values and Change from Baseline for Ambulatory Blood Pressure by Gender (ABP Population)
- Table 14.2.3E Summary of Values and Change from Baseline for Ambulatory Blood Pressure by Age Group (ABP Population)

PROGRAMMING NOTE: Replace Visit with each subgroup as applicable per table title.

Table 14.2.4A

Mixed Model Analysis of Change from Baseline in Daytime Ambulatory Blood Pressure (ABP Population)

Parameter: Systolic Blood Pressure

Time Point	Statistic	4 Sprays (N=xx)		8 Sprays (N=xx)		Placebo (N=xx)	
		Baseline	Day 28	Baseline	Day 28	Baseline	Day 28
Hour 1	n	xx	xx	xx	xx	xx	xx
	Mean (SD)	xx.x (xx.xx)	xx.x (xx.xx)	xx.x (xx.xx)	xx.x (xx.xx)	xx.x (xx.xx)	xx.x (xx.xx)
	Median	xx.x	xx.x	xx.x	xx.x	xx.x	xx.x
	Min, Max	xx, xx	xx, xx	xx, xx	xx, xx	xx, xx	xx, xx
Hour 2	n	xx	xx	xx	xx	xx	xx
	Mean (SD)	xx.x (xx.xx)	xx.x (xx.xx)	xx.x (xx.xx)	xx.x (xx.xx)	xx.x (xx.xx)	xx.x (xx.xx)
	Median	xx.x	xx.x	xx.x	xx.x	xx.x	xx.x
	Min, Max	xx, xx	xx, xx	xx, xx	xx, xx	xx, xx	xx, xx
Hour 3	n	xx	xx	xx	xx	xx	xx
	Mean (SD)	xx.x (xx.xx)	xx.x (xx.xx)	xx.x (xx.xx)	xx.x (xx.xx)	xx.x (xx.xx)	xx.x (xx.xx)
	Median	xx.x	xx.x	xx.x	xx.x	xx.x	xx.x
	Min, Max	xx, xx	xx, xx	xx, xx	xx, xx	xx, xx	xx, xx

Source: [Listing 16.2.6.1](#)

PROGRAM NAME: XXX

DATE: HH:MM/DDMMYYYY

PROGRAMMING NOTE: Continue for Diastolic Blood Pressure. If the subject has results for more than 24 hours in a visit, only the first time point per hour will be included in the analysis.

Repeat for:

Table 14.2.4B Mixed Model Analysis of Change from Baseline in Daytime Ambulatory Blood Pressure by Hypertension (ABP Population)

Table 14.2.4C Mixed Model Analysis of Change from Baseline in Daytime Ambulatory Blood Pressure by Age Group (ABP Population)

PROGRAMMING NOTE: Add column for each subgroup as applicable per table title.

Table 14.2.5

Change in Proportion of Dippers and Nondippers from Baseline to Day 28 Visit (ABP Population)

Treatment	Baseline	Day 28		Total
		Dipper	Nondipper	
4 Sprays (N=xx)	Dipper	xx (xx.x)	xx (xx.x)	xx (xx.x)
	Non-Dipper	xx (xx.x)	xx (xx.x)	xx (xx.x)
	Total	xx (xx.x)	xx (xx.x)	xx (xx.x)
8 Sprays (N=xx)	Dipper	xx (xx.x)	xx (xx.x)	xx (xx.x)
	Non Dipper	xx (xx.x)	xx (xx.x)	xx (xx.x)
	Total	xx (xx.x)	xx (xx.x)	xx (xx.x)
Placebo (N=x)	Dipper	xx (xx.x)	xx (xx.x)	xx (xx.x)
	Nonipper	xx (xx.x)	xx (xx.x)	xx (xx.x)
	Total	xx (xx.x)	xx (xx.x)	xx (xx.x)

Dipper: 10% decrease in daytime ambulatory systolic blood pressure (SBP) versus the daytime ambulatory SBP.

Nondipper: <10% decrease in nighttime ambulatory SBP versus daytime ambulatory SBP.

Note: Percentages are based on the number of subjects in each treatment group. Subjects in the ABP who are missing any component necessary to calculate dipping are excluded from this table.

Source: [Listing 16.2.6.1](#)

PROGRAM NAME: XXXXXXXXXXXXXXXXXXXXXXXXXXXXXXXXXXXXXXX

DATE: HH:MM/DDMMYYYY

Table 14.3.1.1

Overall Summary of Treatment-Emergent Adverse Events (Safety Population)

Statistic	B244				Placebo (N=xx)	Overall (N=xx)
	4 Sprays (N=xx)	8 Sprays (N=xx)	All B244 (N=xx)			
Subjects with at Least 1 Treatment-Emergent Adverse Event (TEAE)	n (%)	xx (xxx.x)	xx (xxx.x)	xx (xxx.x)	xx (xxx.x)	xx (xxx.x)
Subjects with at Least 1 Treatment-Related TEAE	n (%)	xx (xxx.x)	xx (xxx.x)	xx (xxx.x)	xx (xxx.x)	xx (xxx.x)
Subjects with at Least 1 Grade 3 or 4 TEAE	n (%)	xx (xx.x)	xx (xx.x)	xx (xx.x)	xx (xx.x)	xx (xx.x)
Subjects with at Least 1 Treatment-Related Grade 3 or 4 TEAE	n (%)	xx (xx.x)	xx (xx.x)	xx (xx.x)	xx (xx.x)	xx (xx.x)
Subjects with at Least 1 Serious TEAE	n (%)	xx (xx.x)	xx (xx.x)	xx (xx.x)	xx (xx.x)	xx (xx.x)
Subjects with at Least 1 Treatment-Related Serious TEAE	n (%)	xx (xx.x)	xx (xx.x)	xx (xx.x)	xx (xx.x)	xx (xx.x)

If a subject experiences multiple occurrences in the category of Adverse event , the subject will be counted only once for that PT/SOC.

If a subject experiences the same AE more than once with different CTCAE grades, the event with the highest grade will be tabulated. TEAE is defined as any AEs that begin or worsen on or after the start of study drug through 30 days after the last dose of study drug. Treatment-related TEAE is defined as TEAE that was considered by the Investigator to be at least possibly related to the study drug. Severity will be graded based on the NCI CTCAE, Version 4.03.

Adverse events are coded using MedDRA v19.0.

Source: [Listing 16.2.7.1](#)

PROGRAM NAME: XXXXXXXXXXXXXXXXXXXXXXXXXXXXXXXXXXXXXXX

DATE: HH:MM/DDMMYYYY

Table 14.3.1.2

Treatment-Emergent Adverse Events (TEAE) by MedDRA System Organ Class and Preferred Term (Safety Population)

		B244				Overall (N=xx)
Statistic		4 Sprays (N=xx)	8 Sprays (N=xx)	All B244 (N=xx)	Placebo (N=xx)	
Any TEAE	n (%)	xx (xx.x)	xx (xx.x)	xx (xx.x)	xx (xx.x)	xx (xx.x)
System Organ Class 1						
Preferred Term 1	n (%)	xx (xx.x)	xx (xx.x)	xx (xx.x)	xx (xx.x)	xx (xx.x)
Preferred Term 2	n (%)	xx (xx.x)	xx (xx.x)	xx (xx.x)	xx (xx.x)	xx (xx.x)
Etc.						
System Organ Class 2						
Preferred Term 1	n (%)	xx (xx.x)	xx (xx.x)	xx (xx.x)	xx (xx.x)	xx (xx.x)
Preferred Term 2	n (%)	xx (xx.x)	xx (xx.x)	xx (xx.x)	xx (xx.x)	xx (xx.x)
Etc.						

TEAE is defined as any AEs that begin or worsen on or after the start of study drug through 30 days after the last dose of study drug. If a subject experiences multiple occurrences in the same PT/SOC, the subject will be counted only once for that PT/SOC.

Adverse events are coded using MedDRA v19.0.

Source: [Listing 16.2.7.1](#)

PROGRAM NAME: XXXXXXXXXXXXXXXXXXXXXXXXXXXXXXXXXXXXXXX

DATE: HH:MM/DDMMYYYY

Repeat Table 14.3.1.2 for the following tables:

Table 14.3.1.3 Treatment-Related Treatment-Emergent Adverse Events (TEAE) by MedDRA System Organ Class and Preferred Term (Safety Population)

PROGRAMMING NOTE: filter for at least possibly related to the study drug. Add footnote "Treatment-related TEAE is defined as TEAE that was considered by the Investigator to be at least possibly related to the study drug."

Table 14.3.1.4 Grade 3 or 4 Treatment-Emergent Adverse Events (TEAE) by MedDRA System Organ Class and Preferred Term (Safety Population)

PROGRAMMING NOTE: filter for grade = 3 or 4. Add footnote "Severity will be graded based on the NCI CTCAE, Version 4.03." AND "If a subject experiences the same AE more than once with different CTCAE grades, the event with the highest grade will be tabulated."

Table 14.3.1.5 Treatment-Related Grade 3 or 4 Treatment-Emergent Adverse Events (TEAE) by MedDRA System Organ Class and Preferred Term (Safety Population)

PROGRAMMING NOTE: filter for grade = 3 or 4 and at least possibly related to the study drug. Add footnote "Treatment-related TEAE is defined as TEAE that was considered by the Investigator to be at least possibly related to the study drug." AND "Severity will be graded based on the NCI CTCAE, Version 4.03." AND "If a subject experiences the same AE more than once with different CTCAE grades, the event with the highest grade will be tabulated."

Table 14.3.1.6 Serious Treatment-Emergent Adverse Events (TEAE) by MedDRA System Organ Class and Preferred Term (Safety Population)

PROGRAMMING NOTE: filter for SERIOUS = YES.

Repeat Listing 16.2.7.1 for the below table listings.

Table 14.3.2.1 Serious Adverse Events

PROGRAMMING NOTE: filter for SERIOUS = YES and remove Serious? Column.

Table 14.3.2.2 Adverse Events Leading to Early Discontinuation

PROGRAMMING NOTE: filter for subjects who discontinued early.

Table 14.3.2.3 Subject Deaths

PROGRAMMING NOTE: filter for subject deaths, remove Outcome column and accompanying footnote and renumber other footnotes accordingly.

Table 14.3.5.1

Summary of Values and Change from Baseline for Chemistry Parameters (Safety Population)

Parameter: xx

B244									
Visit	Statistic	4 Sprays (N=xx)		8 Sprays (N=xx)		All B244 (N=xx)		Placebo (N=xx)	
		Value	Change from Baseline	Value	Change from Baseline	Value	Change from Baseline	Value	Change from Baseline
Baseline	n	xx	-	xx	-	xx	-	xx	-
	Mean	xx.x		xx.x		xx.x		xx.x	
	(SD)	(xx.xx)		(xx.xx)		(xx.xx)		(xx.xx)	
	Median	xx.x		xx.x		xx.x		xx.x	
	Min, Max	xx, xx		xx, xx		xx, xx		xx, xx	
Day 28	n	xx	xx	xx	xx	xx	xx	xx	xx
	Mean	xx.x	xx.x	xx.x	xx.x	xx.x	xx.x	xx.x	xx.x
	(SD)	(xx.xx)	(xx.xx)	(xx.xx)	(xx.xx)	(xx.xx)	(xx.xx)	(xx.xx)	(xx.xx)
	Median	xx.x	xx.x	xx.x	xx.x	xx.x	xx.x	xx.x	xx.x
	Min, Max	xx, xx	xx, xx	xx, xx	xx, xx	xx, xx	xx, xx	xx, xx	xx, xx

Source: [Listing 16.2.8.1.1](#), [Listing 16.2.8.1.2](#)

PROGRAM NAME: XXX

